We propose to assess the therapeutic potential of TSEC in preventing metabolic dysfunction in postmenopausal women and to explore the hypothesis that the metabolic effect of TSEC relies on the activation of the production and sensitivity of the hepatic hormone fibroblast growth factor 21 (FGF21). These findings will have a direct and immediate scientific impact that fits with the LACaTS Center theme. The knowledge that will be generated from this work will fill key gaps in our understanding of the mechanism of estrogen action on metabolic diseases that will be used for therapeutic purposes. Thus, there is direct, clinically relevant translational impact to the proposed work. As part of this LACaTS grant, [name] will continue to investigate the potential molecular mechanisms of TSEC on the metabolic syndrome in mice only.

There are several innovative features to our proposed study. **First**, a novel feature of our approach is that translational studies of TSEC action in preventing metabolic dysfunction in postmenopausal women have never been performed. A **second**, innovation is to propose a novel paradigm in which the metabolic actions of TSEC are mediated via a stimulation of FGF21 production and action.

STUDY DESIGN

Study Overview

The goal of this pilot clinical study is to perform a **randomized crossover study** to test the beneficial effect of 8 weeks of treatment with TSEC or BZA/CE/(a clinical image of Duavee™) vs. placebo on insulin sensitivity and energy metabolism in eight post-menopausal women. There will be a two-month washout period in-between the 2 treatments (TSEC vs. Placebo). The recruitment will be performed at the Pennington Biomedical Research Center with the help in recruiting from the Baton Rouge General Obstetrics and Gynecology Physicians (see below). The drugs will be provided by Pfizer, Inc. without charge.

Objective: Assess the therapeutic potential of TSEC in preventing metabolic dysfunction in postmenopausal women.

Primary Endpoint: Insulin sensitivity by a 2-step hyperinsulinemic euglycemic clamp

Secondary Endpoints: a) Resting metabolic rate by a metabolic cart (Deltatrac) and;
b) Body composition by DXA and MRS

Exploratory Endpoints: Molecular work (at Tulane) in animal model only.

Hypothesis

TSEC treatment will improve both whole body insulin sensitivity (high insulin dose) and liver insulin sensitivity (suppression of HGP) in postmenopausal women.

Power Calculation

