The glucose clamp will be performed at the end of the two 8-week treatment periods as shown in Figure 2. At approximately 7pm the night before, participants will eat a standard meal (30% of energy requirements calculated on the basis of their (Harris-Benedict predicted RMR x 1.4; 50% CHO, 30% fat, and 20% protein). Between 4am and 7am, a catheter will be inserted into a hand vein heated at 56°C to obtain arterialized blood samples and into an antecubital vein of the contralateral arm for infusion of labeled glucose. Approximately 30 minutes after inserting the IV lines, a skeletal muscle biopsy and an abdominal adipose tissue biopsy will be collected. After baseline blood samples are obtained, [6,6-²H₂]-glucose (22 µmol/kg prime and 0.22 µmol·kg⁻¹·min⁻¹ constant infusion basal) will be started between 4am and 7am. Three hours later, the 2-step euglycemic (20 and 120 mU m⁻² min⁻¹) hyperinsulinemic clamp is initiated and continued for 5 hours. Euglycemia (90 mg/dl) is achieved by a variable infusion of 20% dextrose enriched to approximately 2.0% with [6,6-²H₂]-glucose to minimize changes in glucose isotopic enrichment. The plasma insulin concentrations achieved with these insulin infusion rates provide optimal ranges for evaluating insulin's effect on hepatic glucose production (HGP) (20 mU m⁻² min⁻¹) and glucose uptake by skeletal muscle (120 mU m⁻² min⁻¹). The infusion of [²H₂]-glucose will be decreased by 50% (0.11 µmol·kg⁻¹·min⁻¹) of basal during stage 1 and completely during stage 2 (full suppression of HGP). Three blood samples will be taken during the last 30 min of each step and at each step including baseline, a blood sample will be drawn to be archived (20 ml at baseline and 10 ml at steps 1 and 2).

Calculations. At low dose insulin infusion, plasma insulin levels are expected to increase to ~50 µU/ml, and HGP is expected to be ~50% suppressed in these participants. During this steady state (R_d), peripheral glucose uptake equals the glucose infusion rate (GINF) plus the measured residual HGP (R_d = St-state GINF + residual HGP). At 120 mU m⁻² min⁻¹ of insulin, HGP will probably be totally suppressed, and R_d = Steady State GINF. At each step, insulin sensitivity (SI) will be calculated using the formula: SI = R_d / (St-state insulin level - basal insulin level).

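### Does the single SI formula, which indexes peripheral glucose uptake, leave the liver half of the hypothesis untested?

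*Combined protocol and SAP*

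**What the plan says.** The Study Overview states: "Primary Endpoint: Insulin sensitivity by a 2-step hyperinsulinemic euglycemic clamp". It names no step, organ or index. The Hypothesis supplies the two parts: "TSEC treatment will improve both whole body insulin sensitivity (high insulin dose) and liver insulin sensitivity (suppression of HGP) in postmenopausal women". The Power Calculation paragraph also treats whole-body and hepatic sensitivity as two separate outcomes.

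The clamp section assigns the 20 mU step to insulin's effect on HGP and the 120 mU step to muscle uptake. Study Visits plans three hours of labelled glucose before the clamp to measure basal glucose output. Glucose is then held at 90 mg/dl by a "variable infusion of 20% dextrose enriched to approximately 2.0" percent with the same label, and the separate tracer infusion is reduced by 50% "of basal during stage 1 and completely during stage 2 (full suppression of HGP").

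Under Calculations, the low step has the expectation that "HGP is expected to be ~50% suppressed in these participants", and "peripheral glucose uptake equals the glucose infusion rate (GINF) plus the measured residual HGP". At the high step, "HGP will probably be totally suppressed, and R_d = Steady State GINF". The SI formula follows: "At each step, insulin sensitivity (SI) will be calculated using the formula: SI = R_d / (St-state insulin level - basal insulin level"). Statistical Analysis names a mixed model or another suitable method, adjustment for multiple testing and a significance level of 0.05. It names no hepatic variable.

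**The concern.** The one written formula for insulin sensitivity applies to both steps and has peripheral uptake in the numerator. At the low step, residual HGP enters R_d with a plus sign. At the high step HGP is taken as zero. Neither SI value therefore carries information about the liver.

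If SI were the whole of the primary endpoint, the step chosen to study the liver would yield a second peripheral index. A real hepatic benefit would then appear as no change. Half of the hypothesis would be untested or wrongly called negative, or it would be rescued by a hepatic index chosen after the data were seen. With about 8 to 10 women and an open-ended analysis paragraph, that last risk deserves attention.

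**Working it through.** The plan gives no calculation to reproduce here, so the check is of its formulas.

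**Inputs.** From the plan: low-step insulin about 50 µU/ml; low-step suppression about 50%; tracer 0.22 µmol/kg/min basal and 0.11 at the low step; dextrose enrichment about 2.0%. Assumed: basal insulin 10 µU/ml; uptake 2.5 mg/kg/min; basal HGP about 2.0 mg/kg/min. The last comes from 0.22/0.020 = 11 µmol/kg/min, and 11 x 0.180 = 1.98 mg/kg/min. It assumes that basal plasma enrichment is close to that of the dextrose, which the plan does not say.

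**1. Liver improves, uptake unchanged.** R_d = GINF + HGP and SI = R_d/(50 - 10).

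| Suppression | HGP | GINF | R_d | SI |
|---|---|---|---|---|
| 50% | 1.0 | 1.5 | 2.5 | 0.0625 |
| 60% | 0.8 | 1.7 | 2.5 | 0.0625 |
| 75% | 0.5 | 2.0 | 2.5 | 0.0625 |

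The change in SI is 0%. This is an identity: whatever HGP loses, the variable infusion replaces. It does not depend on the assumed values.

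**2. GINF held at 1.5.** R_d becomes 2.3 at 60% suppression and 2.0 at 75%. SI becomes 2.3/40 = 0.0575 (-8%) and 2.0/40 = 0.0500 (-20%). This looks like a liver benefit read as harm, but it is not a pure liver effect. In a steady-state clamp at fixed glucose, GINF can stay constant while HGP falls only if uptake falls by the same amount, here from 2.5 to 2.3 or 2.0. SI then falls because peripheral sensitivity has fallen, which is what SI should show.

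**3. The measure named in the hypothesis.** Percent suppression = 100 x (1 - low-step HGP / basal HGP). With basal HGP 2.0, the three rows of the table give 100 x (1 - 1.0/2.0) = 50, 100 x (1 - 0.8/2.0) = 60 and 100 x (1 - 0.5/2.0) = 75. The first is the plan's own expected value. Both quantities in the ratio are already to be measured.

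**4. Measurement error in suppression.** Using HGP = (F + GINF x E_inf)/E_plasma - GINF - F, where F is the tracer rate and E_inf the dextrose enrichment, take basal HGP 11, low-step HGP 5.5 and GINF 8.39 µmol/kg/min.

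- *Random error.* A 1% error in each plasma enrichment gives an SD of about 1.4 points from single samples. With three independent samples at both the basal and low steps it is about 1.4/√3 = 0.8.
- *Dextrose enrichment.* If the true value is 2.1% and 2.0% is used, plasma enrichment is 2.044% and HGP reads 5.09, so suppression reads 100 x (1 - 5.09/11) = 53.7%. If the true value is 1.9%, HGP reads 5.94 and suppression 46.0%. Two batches at these extremes would differ by 7.7 points. One batch used in both periods largely cancels the error.

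These errors belong to the tracer method. They are the same whether or not the formula is written down.

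**The case for a change.** The strongest case for a change is that intent is not a definition. Percent or absolute suppression, with or without adjustment for insulin, primary or not: the text settles none of these outright. The plan sets a 0.05 level and expects to detect hepatic improvement, so it means to judge the result, and a sentence or two would cost nothing.

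Part of this stands. The formula and its rank are unwritten. The figure on the clamp procedure is not visible here, so a definition there cannot be ruled out, although the text cites it only for the procedure. But the plan narrows the choice: it speaks of suppression, states it as a percentage, measures the basal value that a percentage needs, and ties it to the low step. Judging the liver half by SI would mean setting aside the Hypothesis.

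The other possible edits add little. Naming high-step SI as the whole-body measure repeats the Hypothesis. Relabelling low-step SI as peripheral repeats the definition of R_d. Requiring both measures to succeed, each at 0.05, would be a new decision rule that the word both in a hypothesis does not impose. It also has a price. At the effect giving 80% power for one test (1.19 SD of the paired difference with 8 women, 1.01 with 10), joint power is about 64%, 68% or 72% for correlations of 0, 0.5 or 0.8. In a pilot with no formal power calculation, that is a debatable trade-off.

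**Conclusion.** The concern does not call for a change. SI does not respond to a pure change in HGP suppression (exactly 0% with uptake and insulin fixed). The apparent falls of 8% and 20% require a real loss of peripheral uptake, so they do not show a liver benefit being misread. The liver measure is already named, assigned to a step and supported by planned basal and low-step tracer data. The usual percent-suppression calculation gives the plan's expected 50% and moves point for point with the liver effect. What remains is an unwritten formula and rank, which a competent analyst would supply from the Hypothesis and the clamp section. This conclusion rests on the plan being read as a whole, and on basal and residual HGP being measured as described. The SI identity needs no assumed values. The illustrative rates and enrichment errors do.

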Although a formal power analysis was not feasible in this pilot study, in light of the high precision that is achieved using the clamp, we can expect similar improvements to be detectable with up to 10 or less completers for whole body and hepatic insulin sensitivity respectively in this randomized crossover trial.

Timeline

After passing the screening process, the expected duration of an individual subject's participation in the study is about 26 weeks.

We anticipate that it will take up to 6 months to complete enrollment for the study.

STUDY POPULATION

Target Population

Post-menopausal women (<5y post last period) aged 50-60 years old

Number of Participants

We expect up to 10 post-menopausal women to complete this study.

Inclusion/Exclusion Criteria

Inclusion Criteria

- Post-menopausal women (<5y post last period)
- Age between 50-60y
- Symptomatic (hot flashes, vaginal dryness) or asymptomatic
- BMI 30-40 kg/m²
- Normal mammogram past 12 months
- Physician clearance (Ob/Gyn, Baton Rouge General Physician Primary Care Network, or PBRC)
- Be willing to accept own blood during IV procedure

Exclusion Criteria

- Amenorrhea other causes (excess androgen)
- Diabetes mellitus
- Medications: (diabetes, antipsychotics, oral steroids, weight loss drugs[†])
- History of major depressive episodes requiring treatment
- Tricyclic antidepressants (TCAs)
- Current smokers, or having smoked within last 3 months
- ≤ 3 month washout of birth control pill, estrogen, and/or progestin
- Hysterectomy (total and partial)
- Contraindications to estrogen treatment ^{††}
- Unable or unwilling to do an MRS
- Additional exclusion for optional BIA procedure only:
 - Medications: Diuretics, glitazones
 - Congestive heart failure
 - Chronic kidney disease
 - Pacemaker or other metal implants

† other chronic medications are acceptable as long as stable for 2 months, and may need MI approval before screening.

†† for unusual vaginal bleeding, blood clots, hepatic disease, bleeding disorder, past/present history of breast or uterine cancer, pregnant, breastfeeding

Recruitment

Baton Rouge General Obstetrics and Gynecology Physicians will be the primary site for recruiting patients for the study. Gynecology and the Baton Rouge General Physician Primary Care Network will also be asked to provide additional recruits through a series of educational

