Prospective volunteers will be both referred from [name] or via PBRC recruitment efforts (see above) and invited to the Center for a complete screening visit conducted in the morning after an overnight fast. Height, metabolic weight, waist and hip circumference as well as blood pressure will be measured. This will be followed by a complete medical history including reproductive function and medications, a physical exam, and an ECG. If eligible, a blood sample (CBC, chemistry panel with electrolytes, total testosterone, estradiol and FSH)

and a urine sample (urine analysis for general health) will be collected. Potential participants will then be interviewed by trained staff that is overseen by a licensed Clinical Psychologist to identify potential barriers to adherence and study completion. We will work with potential participants to determine if the study is consistent with their lifestyle/time demands and if adhering to and completing the study is feasible. The final enrollment will then be determined on the basis of the laboratory results (blood and urine).

Randomization

Participants will be randomized to the order in which they complete the two parts of the study (Active drug (TSEC) and placebo).

[figure not shown]
Study Visits

The study visits are described in this section, while the study procedures that will be performed during these visits are detailed in the latter section “Study Procedures”.

This study involves is a randomized crossover study with two 8-week treatment period separated by an 8-week washout period. Each participant will participate in this randomized scheme with two evaluation periods (see Figure 1)

- a) End of 8 weeks of treatment with PLACEBO or TSEC
- b) End of 8 weeks of treatment with TSEC or PLACEBO

Figure 1. TSEC Experimental Protocol

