Participants should remain resting in the supine position for 10 minutes prior to testing, after voiding, in the fasting state. Once a participant's Subject ID, date of birth, age, sex, height, and weight are entered into the device, the procedure can be conducted. The BIA device automatically tests and analyzes with imbedded software. BIA will be performed according to the recommendations (ESPEN Guidelines, Kyle et al. Clin Nutr 2004). Two disposable BioTekna electrodes will be applied to the dorsal surface of the right hand: the first (injector electrode) on the distal end of the third metacarpal bone between the 2nd and 3rd finger (metacarpophalangeal joint), and the second (sensor electrode) between the distal prominences of the radius and ulna of the wrist (radio-ulnar joint). Another couple of electrodes will be placed on the dorsal surface of the right foot: the first electrode on the distal end of the third metatarsal bone between the 2nd and 3rd toe (metatarsophalangeal joint), and the second electrode between the medial and lateral malleolus of the ankle (tibiotarsal joint).

The distance between the electrodes is 5 cm. Two pairs of cables will be connected to the right hand (it is irrelevant which of the two pairs of cables). Similarly, the other pair of cables will be connected to the right foot. The red alligator clip shall be connected to the injector electrode (metatarsophalangeal joint and metacarpophalangeal joint), while the black clip to the sensor electrode (tibiotarsal joint and radio-ulnar joint). Note: the two pairs of cables should not touch or cross each other, or touch the floor. Failure to observe these precautions may distort the test results.

DATA MANAGEMENT

Data and Biospecimen Storage

Electronic data will be stored securely on computers at PBRC. Paper forms will be kept securely in locked storage at PBRC. Blood samples will be stored in the Clinical Chemistry Core at PBRC. Specimens will be labeled with a unique de-identification code if transported outside of Pennington Biomedical.

Statistical Analysis

Using SAS® Version 9.4 and/or other statistical software, the data will be analyzed using mixed model or other appropriate statistical approaches and using post-hoc comparison adjustments for multi-testing. Descriptive analysis will also be performed. Statistical significance is set at $\alpha=0.05$.

Confidentiality and Privacy

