- **Risks associated with TSEC (Bazedoxifene/Conjugated Estrogens (BZA/CE):** The most common side effects reported in at least 1 out of 100 postmenopausal women receiving BZA/CE include abdominal (stomach) pain, vaginal discharge, vaginal yeast infection, and leg cramps. Other adverse events reported in less than 1 out of 100 subjects were gall bladder disease and increase in liver function tests. More serious but rare side effects associated with the use of BZA/CE included venous thromboembolic events (blood clot in a vein of the legs or lungs), reported in less than 1 out of 100 subjects. If you experience sudden pain in legs or difficulty breathing, notify the Medical Investigator immediately.

Precautions

You may be allergic to conjugated estrogens or bazedoxifene. If you experience allergy symptoms such as rash, hives, or itching, notify your study doctor immediately.

All estrogens and SERMS should be stopped prior to and during prolonged

immobilization (such as bed rest, surgery or long-distance travel). It is recommended that study drug be discontinued four to six weeks prior to prolonged immobilization.

You may not use hormone products during the study; including any oral, transdermal, vaginal or other products containing estrogens, progestins, androgens, testosterone, DHEA or SERMs.

- **Blood Draws:** There is the possibility of discomfort, pain, and bruising at the arm vein or site where the needle is inserted. There is also a small risk of bleeding and a very small risk of infection at the site of the blood draw. Aseptic (sterile) technique and trained personnel minimize these risks.
- **DXA:** The DXA scan involves extremely low levels radiation exposure. This technique has been demonstrated to be safe and approved for children. There are no known risks of the body scan.

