- **Bioelectrical Impedance Analysis (BIA):** There is no risk associated with the BIA measurement provided that prescreening is performed to exclude individuals with medical implants such as pacemakers or metal joint replacements. Measurements will not be performed on any subject who is pregnant, and all females should inform the technologist if there is any possibility that they are pregnant.

In addition to the risks listed above, participants may experience a previously unknown risk or side effect.

Monitoring Subject Safety

Participants will be asked about any adverse events following each stay in the respiratory chamber. Any instances adverse events and safety concerns will be documented and reported to the PBRC IRB per standard procedures.

Once every 4 months, the PI will review the progress and safety of the study with the MI, and write a summary of the results of those discussions as applicable.

Compensation

Participants will be compensated \$1000 if they complete the entire study. \$350 of the compensation will be paid at the end of their first phase treatment and the remaining \$650 at the end of the study. There is no compensation available for research-related injury.

Withdrawal of Subjects

There is no risk associated with withdrawal from TSEC. Participants may be withdrawn from the study if either the PI or MI feels that their continued participation would jeopardize either the subject's health or the results of the study.

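### Could the investigators' freedom to withdraw a woman to protect the study's results bias the crossover comparison?

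*Combined protocol and SAP*

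**What the plan says.** Withdrawal of Subjects (combined protocol and SAP) reads "Participants may be withdrawn from the study if either the PI or MI feels that their continued participation would jeopardize either" the participant's "health or the results of the study". The health ground is not in question. No criteria are given for the other ground. Nothing is said about who holds what information when the decision is made, or about data already collected.

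The design is a two-period crossover: "Participants will be randomized to the order in which they complete the two parts of the study". On the primary endpoint, the clamp section says "The glucose clamp will be performed at the end of the two 8-week treatment periods", and no pre-treatment clamp is described. A woman who leaves between periods therefore contributes one clamp and no within-woman difference.

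Statistical Analysis says that "the data will be analyzed using mixed model or other appropriate statistical approaches", with significance at 0.05. It defines no analysis set and no missing-data rule. Power Calculation speaks of detectability with "up to 10 or less completers". A placebo is used, but the public text, which lacks some pages, does not say who is masked.

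**The concern.** A withdrawal clause that rests on what an investigator feels about the results invites suspicion. The first clamp falls at about week 8 and the second at about week 24 (8 + 8 + 8), so for some 16 weeks a primary result exists while the discretion is open. If a woman with a poor clamp on TSEC, or a very good one on placebo, were withdrawn in that interval, and the trial then analysed complete pairs only, the remaining women would favour TSEC even with no drug effect. With 8 to 10 women, one exclusion is a visible share of the data. Neither an objective list of reasons, nor a masked decision, nor a promise to keep the first clamp is written down.

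**Working it through.** The plan gives no SD, effect size, dropout rate or power, so there is no figure of its own to reproduce. What can be checked is how large the bias would be, and under which conditions.

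**Inputs from the documents.** n = 8 (Study Overview) or up to 10 (Number of Participants); randomised order; one clamp per period; alpha 0.05, taken as two-sided because the side is not stated.

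**Assumptions.** Normal data, no true effect unless stated, no period or carryover effect, within-woman correlation rho of 0.5, 0.7 or 0.9, and one woman withdrawn after her first clamp. Results are in SDs of the paired difference, SDd, unless noted.

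**1. Treatment known, complete pairs only.** Score each first clamp so that low is unfavourable to TSEC: its value if TSEC came first, minus its value if placebo came first. With no effect these n scores are independent standard normal. For n = 8 the lowest has mean -1.4236. Given her score, a woman's expected TSEC-minus-placebo difference is (1 - rho) times the score, and SDd = sqrt(2(1 - rho)). Removing her shifts the mean of the other 7 by

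bias = (1.4236 / 7) × (1 - rho) / sqrt(2(1 - rho)) = 0.2034 × sqrt((1 - rho)/2)

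- rho 0.5: 0.2034 × 0.500 = 0.102
- rho 0.7: 0.2034 × 0.387 = 0.079
- rho 0.9: 0.2034 × 0.224 = 0.045

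Simulation (300,000 null trials per setting, paired t) agrees and adds the error rates:

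| n | rho | bias (SDd) | false positives favouring TSEC (nominal 2.5%) | two-sided (nominal 5%) |
|---|---|---|---|---|
| 8 | 0.5 | 0.102 | 4.5% | 6.1% |
| 8 | 0.7 | 0.079 | 3.9% | 5.6% |
| 8 | 0.9 | 0.046 | 3.3% | 5.2% |
| 10 | 0.5 | 0.086 | 4.4% | 6.0% |
| 10 | 0.7 | 0.066 | 3.9% | 5.6% |
| 10 | 0.9 | 0.039 | 3.2% | 5.2% |

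This removes the most unfavourable woman of all. A milder rule, removing the lowest clamp among TSEC-first women only, gives a bias of 0.03 to 0.08 and 2.9% to 3.8% favouring TSEC.

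**2. Treatment not known, complete pairs only.** If the lowest first clamp is withdrawn regardless of sequence, the bias is 0.00 and the two-sided error 4.9% to 5.0%, provided there is no true effect. With a true effect of 1 SDd, placebo-first women tend to have the lower first clamps and are withdrawn more often. The bias is then -0.05, -0.03 and -0.01 at n = 8, and -0.04, -0.03 and -0.01 at n = 10, for rho 0.5, 0.7 and 0.9. So masking does not remove all bias from complete pairs, but what remains is small and runs against TSEC.

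**3. Treatment known, first clamp kept.** The withdrawal then depends only on data in the model (first clamp, treatment, period), so a likelihood analysis remains valid. REML with treatment and period (40,000 trials; t reference with complete pairs minus 2 degrees of freedom, an assumption) gives:

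- n = 8: bias -0.002, -0.009, -0.007; favouring TSEC 3.4%, 3.1%, 2.9%; two-sided 5.5%, 5.2%, 5.3%.
- n = 10: bias 0.002, -0.004, -0.004; favouring TSEC 3.0%, 3.0%, 2.9%; two-sided 5.1%, 5.2%, 5.1%.

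**4. Scale.** With 7 complete pairs the 95% interval has expected half-width of about t(0.975, 6)/sqrt(7) = 2.4469/2.6458 = 0.925 SDd. The worst bias in the table is 0.102/0.925, or 11% of that.

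**The case for a change.** The strongest argument for acting is that the text commits to neither safeguard and a few sentences would supply both. At the high insulin dose, if hepatic glucose production is fully suppressed, glucose uptake equals the infusion rate, so the main part of the result can be read at the bedside. The PI and MI also meet every four months, and no masking of that review is stated. The analysis wording leaves room for something other than a mixed model. A second informed withdrawal makes matters worse: removing the lowest TSEC-first and the highest placebo-first woman gives a complete-pairs bias of 0.07 to 0.17 SDd, with 3.6% to 5.8% favouring TSEC and 5.3% to 7.0% two-sided.

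The omissions and the arithmetic stand. The inference from them does not. Silence on masking in a placebo-controlled crossover is not evidence that the decision is made unmasked, and nothing says that clamp results are discussed at the four-monthly review. The completers appear in the power paragraph, where they describe detectability; they do not define the analysis set. The withdrawal clause looks forward, to continued participation, and discards nothing already measured. It also has plain uses, such as breach of the rule under Precautions: "You may not use hormone products during the study". The two-withdrawal case still needs complete pairs: keeping the first clamp in a likelihood model brings the bias to between -0.02 and +0.01 SD of a single clamp, about zero within simulation error.

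The proposed remedies also gain little. A masked adjudicator is extra staff for a hypothetical misuse and, by step 2, would not make complete pairs unbiased under a real effect. Keeping the clamp barely changes the two-sided error at high correlation (n = 8, rho 0.9: 5.2% for complete pairs, 5.3% for REML).

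**Conclusion.** No change is needed. This is a conventional discretion clause beside a brief analysis section, and the unstated point, what to do with an unpaired first clamp, has an ordinary answer within the plan: fit the mixed model to every evaluable clamp. The same answer covers voluntary dropout, which leaves the same unpaired clamp, so the withdrawal wording creates no separate problem.

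The bias figures are conditional. They rest on normal data, correlations of 0.5 to 0.9, withdrawal of the single most unfavourable woman and, for the lean toward TSEC, no true effect, together with the two conditions the documents do not establish. Even then the shift is at most about a tenth of an SDd in a pilot that claims no formal power. The conclusion would differ only if the trial were shown to have made such withdrawals with treatment and first clamp known, and then to have reported complete pairs alone. That would be a question about its conduct and reporting, since the plan calls for neither.
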